**Biochemical abortion associated preferred terms**

Biochemical pregnancy

The relevant preferred terms associated with ectopic pregnancy are listed below. This is based on MedDRA version 21.0. Prior to dry-run and DBL, the dictionary will be checked to make sure there is no change of terms with dictionary update.

**Ectopic pregnancy associated preferred terms**

Abortion of ectopic pregnancy

Ectopic pregnancy

Ectopic pregnancy termination

Ectopic pregnancy under hormonal

contraception

Ectopic pregnancy with contraceptive device

Ruptured ectopic pregnancy

The relevant preferred terms associated with adverse events of special interest ([Appendices 2, 3, and 4 of the Protocol](#)) are listed below. This is based on MedDRA version 21.0. Prior to dry-run and DBL, the dictionary will be checked to make sure there is no change of terms with dictionary update.

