8.3.7 Pregnancy Losses

Cases of biochemical abortion, spontaneous abortion, ectopic pregnancy and heterotopic pregnancy will be recorded as AEs.

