## Secondary Endpoints

- Cumulative rate of spontaneous abortions determined at 6 and 10 weeks post-oocyte retrieval in all subjects treated with PVR.
- Cumulative rate of biochemical abortions determined at 6 and 10 weeks post-oocyte retrieval in all subjects treated with PVR. Biochemical abortion is defined as a positive  $\beta$ -hCG test at 2 weeks and 2 weeks + 3-4 days post-oocyte retrieval, but followed by no observed gestational sac on a later TVUS, or followed by a negative  $\beta$ -hCG test.
- Rate of ectopic and heterotopic pregnancies in all subjects treated with PVR following oocyte retrieval.
- Rate of abnormal findings in clinical laboratory tests and vital signs for all subjects treated with PVR.
- Frequency, intensity/grade, seriousness, and relatedness of adverse events (AEs) for all subjects treated with PVR.
- Frequency, intensity/grade of vaginal bleeding/spotting, vaginal hemorrhage, pain, vaginal infection, and vaginal irritation for all subjects treated with PVR.
- Frequency, intensity/grade, seriousness, and relatedness of AEs associated with vaginal and cervical abrasions and lesions and with vaginal adhesions for all subjects treated with PVR.
- Frequency and reason for PVR discontinuation.
- Positive  $\beta$ -hCG rate (positive serum  $\beta$ -hCG test) at 2 weeks and 2 weeks + 3-4 days post-oocyte retrieval in all subjects treated with PVR.
- Clinical pregnancy rate (TVUS showing at least 1 intrauterine gestational sac with fetal heartbeat) at 6 and 10 weeks post-oocyte retrieval in all subjects treated with PVR.

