### 9.4.3 Ectopic and Heterotopic Pregnancies

At time of TVUS examination, ectopic and heterotopic pregnancies may be detected and recorded in the TVUS eCRF. These events may also occur outside such assessment visits and may be recorded in the AE CRF. The preferred terms associated with ectopic pregnancy are presented in [Appendix 3](#) and will be used to select and check for such terms. The frequency and proportion of subjects with ectopic and heterotopic pregnancies will be pooled from the two sources and summarized.

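### The AE search for the ectopic and heterotopic pregnancy endpoint names no heterotopic term, so a case recorded only as an AE is left out unless it codes to a listed ectopic term

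*SAP*

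**What the plan says.** The endpoint names two events. SAP 2.2 gives it as "Rate of ectopic and heterotopic pregnancies in all subjects treated with PVR following oocyte retrieval".

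SAP 9.4.3 describes two sources. The first is the ultrasound form: "ectopic and heterotopic pregnancies may be detected and recorded in the TVUS eCRF". The second is the AE page: "These events may also occur outside such assessment visits and may be recorded in the AE CRF". For the second source, the ectopic preferred terms in Appendix 3 "will be used to select and check for such terms". The result is then combined: "The frequency and proportion of subjects with ectopic and heterotopic pregnancies will be pooled from the two sources and summarized".

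Appendix 3 introduces the list with "The relevant preferred terms associated with ectopic pregnancy are listed below" and, under the heading "Ectopic pregnancy associated preferred terms", gives six terms: ectopic pregnancy itself, its abortion, its termination, its rupture, and two for ectopic pregnancy in women using contraception.

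The protocol makes the AE page a required route for both events. Section 8.3.7 states: "Cases of biochemical abortion, spontaneous abortion, ectopic pregnancy and heterotopic pregnancy will be recorded as AEs". Protocol 9.7.3.3 likewise has both reported as AEs.

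**The concern.** The SAP promises a pooled count of two events but gives an AE selection rule that names only one. The AE source is there to catch what the scheduled scans do not, and in that source heterotopic pregnancy has no search term of its own.

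If the coding dictionary places a heterotopic pregnancy outside the six listed terms, a case known only from the AE page drops out of a named safety endpoint. Protocol section 2 and SAP section 2 say that the trial is judged on its safety information as a whole. With an event this infrequent, one case changes the reported rate visibly.

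**Working it through.** The plan states no figure for this endpoint, so there is none to reproduce. The check is a count of terms, a walk through the routes by which a case can reach the endpoint, and a scale for one missed case.

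**1. Count of terms.** The Appendix 3 ectopic block has 6 terms, of which 0 contain the word *heterotopic*. The spontaneous abortion, biochemical abortion and special-interest blocks also contain 0.

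**2. Routes into the endpoint for a heterotopic pregnancy.**

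| How the case is recorded | Counted under SAP 9.4.3? |
|---|---|
| On the ultrasound form | Yes; no term list is needed |
| On the AE page only, coded to one of the six terms | Yes |
| On the AE page only, coded to any other term | No |

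Only the third row is a gap. Whether it can occur depends on the coding, which the documents do not give.

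**3. Can a case be on the AE page only?** SAP 9.4.3 itself expects events outside the assessment visits. Pregnancy scans are scheduled at 4 weeks + 3-4 days and at 6 weeks after retrieval and, for women still pregnant, at 10 and 12 weeks (Protocol 6.3.6 to 6.4). The scans from 6 weeks on are specified as counts of gestational sacs with and without heartbeat. If the extrauterine pregnancy was treated between visits, a later scan may show only the intrauterine sac; this is an inference. A woman who withdraws because she is no longer pregnant needs no ultrasound (Protocol Table 6-1, footnote j). The documents do not say whether unscheduled scans go on the ultrasound form. If they do, the gap is narrower still.

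**4. Would another step in the plan catch the case?**
- The dictionary check in Appendix 3 looks for listed terms that have changed with an update. It does not look for a concept that was never listed.
- The pregnancy-loss listing for the medical team (SAP 9.2) is also generated from Appendix 3 terms, and its purpose is to identify spontaneous abortions.

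Neither closes the third row.

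**5. Scale.** One missed case lowers the rate by 1/N, where N is the number of PVR-treated women. The plan gives no figure for N. With N = 240, the planned mITT size used as a stand-in, 1/240 = 0.42 percentage points. Exact (Clopper-Pearson) 95% intervals for N = 240:

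| Cases counted | Rate | 95% CI |
|---|---|---|
| 0 | 0.00% | 0.00 to 1.53% |
| 1 | 0.42% | 0.01 to 2.30% |
| 2 | 0.83% | 0.10 to 2.98% |
| 3 | 1.25% | 0.26 to 3.61% |

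The treated group includes women who received a ring but had no transfer, so it can exceed the mITT cohort. As an assumed upper figure, take the ratio in Protocol 3.5.1 (about 240 enrolled for 215 transfers) and suppose that every enrolled woman was treated. Then 240 transfers go with 240 × 240/215 = 268 treated women, and one case is 1/268 = 0.37 points. The range is thus about 0.37 to 0.42 points per missed case.

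**The case against.** The strongest reply is that the list holds dictionary preferred terms, not words as reported. The absence of the word does not show that the concept is absent: if the dictionary codes heterotopic pregnancy to one of the six terms, nothing is lost. This stands. The documents do not settle it, so the point is about a case that can be missed, not one that will be.

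The second reply is that the gap is narrow. The ultrasound form records heterotopic pregnancy directly, and a woman with one may stay in the trial at the investigator's discretion (Protocol 7.1.1.3) and be scanned again. An AE outside the list would still appear in the treatment-emergent AE table by preferred term and in the phase listings (SAP 10.2.2) and, if serious, in a narrative (SAP 10.2). This also stands: the case would be lost from one endpoint count, not from the safety report.

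A reader might infer more than the documents support:

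- *That the AE source covers only half the endpoint.* This counts the words in the endpoint's name. No document gives the relative frequency of the two events.
- *That the two events could not be told apart if coded to one term.* Protocol 8.2.2 has each AE described, as a diagnosis where available, one per record, and SAP 9.2 shows that reported and coded terms are both available. The reported term would separate them.
- *That the rate would be cut by some set fraction, such as one third.* Any such figure needs an invented split of cases, plus the assumption that the heterotopic case is on the AE page only and coded elsewhere.
- *That the two contraception terms are an error.* Surplus terms in a search list do no harm.
- *That the primary endpoint is at risk because a woman with a heterotopic pregnancy may remain in the trial.* The ectopic list does not determine the primary endpoint.

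**Conclusion.** The concern holds in a limited form. The AE selection rule for a two-event endpoint names one event, and no other step in the plan makes up for it. A heterotopic pregnancy recorded only as an AE and coded outside the six terms would be left out of the count.

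The size is about 0.4 percentage points per missed case, with the denominator taken as roughly 240 treated women and possibly larger. The number of such cases is unknown and probably very small. An actual undercount rests on two conditions that the documents do not establish: that a case is on the AE page only, and that its code lies outside the list.

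This is a minor point. It touches one descriptive secondary endpoint and leaves the primary analysis and the sample size unchanged. It is worth acting on because the repair is almost free and works however the event is coded.

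**What to change.** Before database lock:

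1. In SAP Appendix 3, look up where heterotopic pregnancy codes in the dictionary version used, and add that preferred term to the ectopic block. If it codes to a term already listed, say so in one sentence. The check already planned before the dry run and database lock is a natural place for this.
2. In SAP 9.4.3, add that the reported (verbatim) AE terms will also be searched for the word *heterotopic*, and that each woman is counted once across the ultrasound and AE sources. The section already counts subjects, so the second part only makes the rule explicit.

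Separate rows for ectopic and heterotopic pregnancy are optional; the endpoint is planned as one combined rate.

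The cost is a line in the term list, a sentence or two in SAP 9.4.3 and a short text search. It needs no new data collection and no change to the sample size.

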**Preferred terms associated with adverse events of special interest**

Vulvovaginal pain

Dyspareunia

Vulvovaginal discomfort

Vulvovaginal pruritus
Vulval oedema
Vulvovaginal erythema
Vulvovaginal rash
Bartholin's cyst
Urethral cyst
Vulval disorder
Vaginal oedema
Vulvovaginal dryness
Vaginal discharge
Vaginal erosion
Vaginal lesion
Cervix oedema
Cervical friability
Cervix erythema
Cervical discharge
Cervix disorder
Vulvovaginal adhesion
Vaginal haemorrhage
Vaginal infection
Uterine cervical erosion

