There are 3 analysis cohorts for this trial. The mITT cohort consists of all subjects who had successful oocyte retrieval, received at least 1 dose of IMP, and had completed fresh embryo transfer. The safety cohort comprises all subjects treated with IMP. The eligible subjects (ES) cohort consists of all subjects who were deemed eligible for trial participation based on inclusion and exclusion criteria at screening and treated with oral contraceptives, leuprolide acetate, or MENOPUR.

The primary objective is to estimate the cumulative rate of any spontaneous abortion, including spontaneous clinically recognized pregnancy loss and blighted ovum during the trial (up to Week 12 following oocyte retrieval) for subjects in the mITT cohort. The number and rates of any spontaneous abortions will be summarized and associated exact 95% confidence intervals will be generated. Furthermore, as part of a Bayesian sensitivity analysis, a 95% credible interval will be generated. The spontaneous abortion rate, biochemical abortion rate, clinical pregnancy rate, and positive β -hCG rate will be similarly analyzed for the mITT and safety cohort, for subjects that had oocyte(s) retrieved. However, for these endpoints, credible intervals will not be derived. Furthermore, safety will be assessed by summarizing treatment-emergent AEs for the safety and ES cohorts. Treatment-emergent AEs will be summarized overall, by grade (intensity), seriousness, and drug relatedness by system organ class and preferred term using the Medical Dictionary for Regulatory Activities. A treatment-emergent AE is any AE that occurs after the start of PVR and through the end of the trial, or a pretreatment AE/medical condition that worsens in intensity after the start of PVR. Furthermore, a separate treatment-emergent AE summary table will be generated for AEs of special interest, such as vaginal pain and irritation, vaginal infection, vaginal bleeding/spotting, vaginal hemorrhage, vaginal adhesions and vaginal or cervical abrasions and lesions. These events will also be further analyzed by grade (intensity). Tolerability for the safety cohort will be assessed by summarizing the total number of subjects who prematurely discontinued PVR and the associated reasons for discontinuation. This summary will be based on the safety cohort.

For the safety and ES cohorts, the number of subjects with abnormal clinical laboratory and vital sign assessments will be summarized.

TABLE OF CONTENTS

SYNOPSIS.....	2

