Appendix 3 Assessment of AEs of Special Interest: Vaginal Pain and Vaginal Irritation

[figure not shown]
INDIVIDUAL SIGNS/SYMPOTOMS				
PARAMETER	GRADE 1 MILD	GRADE 2 MODERATE	GRADE 3 SEVERE	GRADE 4 POTENTIALLY LIFE- THREATENING
VAGINAL PAIN				
Pain	Pain causing no or minimal inference with usual social & functional activities	Pain causing greater than minimal inference with usual social & functional activities or the need for non-narcotic medication	Pain causing inability to perform usual social & functional activities or the need for narcotic medication	Disabling pain causing inability to perform basic self-care functions OR hospitalization (other than emergency room visit) indicated
Dyspareunia (pain with sexual activity)	Pain causing no or minimal inference with sexual function	Pain causing greater than minimal inference with sexual function	NA	NA
VAGINAL IRRITATION				
Vaginal itching	Itching causing no, mild or moderate inference with usual social & functional activities	Itching causing inability to perform usual social & functional activities; may require intervention such as antihistamine or bathing to provide relief	NA	NA
Vaginal dryness	Dryness causing no or minimal inference with usual sexual, social & functional activities	Dryness causing greater than minimal inference with usual sexual, social & functional activities	NA	NA
Vaginal discharge by participant report	Mild-moderate increase in amount above participant baseline – no sanitary protection required	Profuse increase in discharge requiring pad use or other hygienic intervention	NA	NA

Adapted from: Division of AIDS Table for Grading the Severity of Adult and Pediatric Adverse Events, Addendum 1 (Female Genital Grading Table for Use In Microbicide Studies); November 2007.

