### **10.2.3 Treatment-Emergent AEs of Special Interest**

Standardized criteria will be applied to some AEs of special interest to establish intensity/grade. For AEs associated with vaginal bleeding/spotting, vaginal pain and irritation, and vaginal or cervical abrasions and lesions, standardized criteria will be used by the sites to record the intensity of these AEs (Protocol Section 8). For these AEs and AEs associated with vaginal hemorrhage, vaginal infection and vaginal adhesions, a summary table of the treatment-emergent AEs of special interest will be produced by preferred term, grade (intensity), and seriousness for subjects in the safety cohort for the treatment phase and the study phase. These AEs will be identified using preferred terms.

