#### **10.4.3 Pelvic Examination**

A pelvic examination will be performed at screening, Visits 4, 7P, 8, 9, and 10 to document the presence and grade (intensity) of any pain, irritation, abrasions, or lesions on the cervix or vagina using standardized criteria, and the presence and grade (intensity) of any vaginal adhesions using standardized criteria. If any lesions or abrasions are found on the cervix or vagina or vaginal adhesions are noted, another examination will be performed 2-4 days later. The grade (intensity) for each type of assessment will be summarized by visit for the safety cohort. Furthermore, a shift table will be presented summarizing the change in grade (intensity) from Visit 4 to the End-of-trial, where the End-of-trial is defined to be the last assessment in the treatment phase.

An associated listing will also be produced.

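### The planned table of adverse events of special interest runs by preferred term and specifies no count of women per category, so vaginal irritation, vaginal pain and abrasions/lesions cannot be read from it

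*SAP*

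**What the plan says.** The secondary endpoints (SAP 2.2, same wording in Protocol 2.2) are defined by clinical category. One is "Frequency, intensity/grade of vaginal bleeding/spotting, vaginal hemorrhage, pain, vaginal infection, and vaginal irritation for all subjects treated with PVR". Another begins "Frequency, intensity/grade, seriousness, and relatedness of AEs associated with vaginal and cervical abrasions and lesions" and goes on to include vaginal adhesions.

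The analysis is set out in SAP 10.2.3. It names the categories of interest and then says that one summary table "will be produced by preferred term, grade (intensity), and seriousness for subjects in the safety cohort". On selection it says "These AEs will be identified using preferred terms". Protocol 9.9.2.1 describes the same table layout. The protocol synopsis says that "a separate treatment-emergent AE summary table will be generated for AEs of special interest, such as vaginal pain and irritation", followed by the other categories and a further analysis by grade.

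The terms are in SAP Appendix 3 under the heading "Preferred terms associated with adverse events of special interest". None is assigned to a category. The other lists in that appendix (spontaneous abortion, biochemical abortion, ectopic pregnancy) each carry the heading of a single endpoint.

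**The concern.** The endpoint asks how many women had, for example, vaginal irritation, and how severe it was. The table answers a different question: how many women had each coded term. A woman with pruritus and discharge is counted in two rows, possibly at different grades. The rows therefore cannot be added, and her worst grade within irritation cannot be recovered from them.

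Local tolerability of the ring is a central question of this trial, and Protocol 1.2 says that adverse event collection and scoring were changed at the Agency's request. If the plan is followed as written, a reader gets a set of small rows and no rate for three named endpoints. If the grouping is made later, it will be made in an open-label trial with the data in view, and several terms could go in more than one category.

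**Working it through.** The documents state no figure for this analysis, so there is none to reproduce. The check has three parts.

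**1. Count and group the terms.** SAP Appendix 3 lists 24 distinct preferred terms. Its text refers back to Protocol Appendices 2, 3 and 4, and the order broadly follows Protocol Appendix 2. Grouping by position against the Protocol Appendix 2 blocks gives:

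| Category | Listed terms | Number |
|---|---|---|
| Pain | vulvovaginal pain, dyspareunia, vulvovaginal discomfort (in the position of tenderness) | 3 |
| Irritation | vulvovaginal pruritus, erythema, rash and dryness; vulval and vaginal oedema; vaginal discharge; Bartholin's cyst; urethral cyst; cervix oedema and erythema; cervical friability and discharge | 13 |
| Abrasions/lesions | vulval disorder, vaginal erosion, vaginal lesion, cervix disorder, uterine cervical erosion | 5 |
| Adhesion, hemorrhage, infection | one term each | 3 |

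Total: 3 + 13 + 5 + 3 = 24.

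The grouping is not unique. Without vulvovaginal discomfort, pain has 2 terms. Protocol 8.3.1 directs adverse events of vaginal pain and irritation to Protocol Appendix 3, where the block headed "Vaginal Irritation" has three items: itching, dryness and discharge. On that definition irritation has 3 listed terms. Protocol 8.3.1 keeps Protocol Appendix 2 for examination findings, but a note there says that clinically significant findings after the start of treatment are also reported as adverse events. Both definitions can therefore feed the same table.

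**2. Bound the category count.** Let x_j be the number of women in row j, U the number with at least one term in the category, and n the size of the safety cohort. Then

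max(x_j) ≤ U ≤ min(n, Σ x_j).

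The lower bound is full overlap between rows and the upper bound is none. The documents give no adverse event rates, so the per-term rates below are assumptions. I use n = 240, the planned mITT size; the safety cohort is at least as large if that target is met.

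| Assumed rate per term | Women per row | 2 terms | 3 terms | 5 terms |
|---|---|---|---|---|
| 1% | 2 | 2–4 (0.8–1.7%) | 2–6 (0.8–2.5%) | 2–10 (0.8–4.2%) |
| 2% | 5 | 5–10 (2.1–4.2%) | 5–15 (2.1–6.25%) | 5–25 (2.1–10.4%) |
| 4% | 10 | 10–20 (4.2–8.3%) | 10–30 (4.2–12.5%) | 10–50 (4.2–20.8%) |

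Before rounding to whole women, three terms at 4% give 4% to 3 × 4% = 12%. If the terms were independent, the rate would be 1 − 0.96³ = 11.5%. With k equally frequent terms, the table leaves the category count open by a factor of up to k.

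The choice of appendix matters as well. At 1% per term, irritation is 2 to 6 women with 3 terms and 2 to 13 × 2 = 26 women (10.8%) with 13.

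**3. Look for another output that gives the count.**
- The general tables in SAP 10.2.2 are by system organ class and preferred term, not by endpoint category.
- For the pelvic examination, SAP 10.4.3 says "The grade (intensity) for each type of assessment will be summarized by visit for the safety cohort", with a shift table from Visit 4 to End-of-trial. These are examination findings by visit, not the number of women with an adverse event over the trial.
- Relatedness belongs to the abrasions/lesions and adhesions endpoint but is not a dimension of the table in SAP 10.2.3. Causality appears only in the general table of SAP 10.2.2.

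**The case against.** The strongest reply is that this is a matter of table layout in a single-arm, descriptive safety trial. No hypothesis or decision rule uses these categories. All the data are collected, and subtotals can be programmed at any time. The sentence that sets up the table names the categories, the list loosely follows the Protocol Appendix 2 blocks, and the pelvic examination summary covers the same ground by visit.

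Much of this stands, and it limits the point. A reader might infer that the category counts can never be obtained. The documents do not support that: the counts are unspecified, but they can be derived from subject-level data. A reader might also fear that the terms vanish because each falls below the 5% incidence tables. They do not: neither the special-interest table nor the table of all treatment-emergent events has a threshold. For pain, the Protocol Appendix 2 footnote asks for only the worse of pain and tenderness when both are present, which limits double counting.

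What the reply does not supply is the rule. Naming categories in a sentence assigns no term to any of them, and the two protocol appendices define irritation differently. Vulvovaginal discomfort, vulval disorder, cervix disorder, Bartholin's cyst and urethral cyst have no settled place.

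**Conclusion.** The point holds for three secondary endpoints: vaginal pain, vaginal irritation, and vaginal/cervical abrasions and lesions. Neither document specifies a count of women for these categories, and the planned table does not determine one. Adhesion and infection have one listed term each, so the row is the count. Hemorrhage has its own eCRF-based count in SAP 10.4.2.

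The term counts and the bounding formula rest on the documents and on arithmetic. The 4% to 12% range is an illustration that rests on an assumed 4% for each of three terms. It is tempting to say that irritation is scattered over more than half of the list and to quote a correspondingly wider range. That reading relies on the examination blocks of Protocol Appendix 2, whereas Protocol 8.3.1 points adverse events of irritation to Protocol Appendix 3, which has three items. The documents leave the number of irritation terms at 3 or about 13 without saying which applies.

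The primary endpoint and the sample size are untouched. This should be corrected because named endpoints would otherwise go unreported in the form in which they are defined.

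**What to change.** Before database lock:

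- Add a column to SAP Appendix 3 that assigns each of the 24 terms to one endpoint category. State whether Protocol Appendix 2 or Protocol Appendix 3 governs irritation for adverse events, and place the five ambiguous terms explicitly.
- In SAP 10.2.3 add, for each category, the number and percentage of safety-cohort women with at least one event. Count each woman once, by worst grade and by seriousness, and show the preferred-term rows beneath.
- For abrasions/lesions and for adhesions, add relatedness, which the endpoint requires.

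The cost is SAP wording and one extra summary level, with no new data and no change to trial procedures. Each category rate will be at least as high as any single-term row within it, and the report should say that this follows from the counting rule.
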